### *Measurements and psychometric instruments*

Assessments in the study are: the screening (for the eligibility interview), the pre-intervention assessment, five weekly measurements during the course (w. 1-5) and the post-intervention assessment. A follow-up assessment will also take place after 3 months. Thus, in total, there are 9 assessment points. The measurements are conducted using online questionnaires that are stored in the patient's digital record.

At the pre-intervention assessment, information is also collected during the eligibility interview. This interview involves questions about sociodemographic variables, a structured questionnaire for the assessment of suicidal ideation and severe psychiatric problems and questions concerning medication.

[Translated from the original that was approved by the Swedish ethical review authority]

At each group session, the participation of each patient is registered. Post intervention, the patient also meets with a clinician of the psychosocial team. This appointment is booked 6 weeks from the planned start of the course. This assessment is conducted in a manner analogous to routine care assessment by the psychosocial team of the primary care clinic. During this assessment, all further necessary arrangements are registered (e.g., no need for further arrangements, referral to psychiatric services or additional help and if so of what kind). The patient also reports on adverse events, satisfaction with the course, changes to medication and other therapies. Lifestyle behaviours are surveyed over the course of the study because little is known about lifestyle behaviours in Swedish primary care patients, and the relation between lifestyle behaviours and mental health has been identified by the Swedish national board of health and welfare as a high-priority topic in primary care research.

Suicidal ideation is monitored during the course of the study. Each week, patients rate how much they are bothered by "thoughts that [they] would be better off dead, or of hurting [themselves]". Patients who score higher than "not at all" are contacted for an individual assessment, and are offered additional support and/or are referred to specialist care in accordance with common practice and routine care guidelines. Each week, patients are also tasked with answering an open-ended question about adverse events. Adverse events are highlighted in the system for data collection and prompt subsequent review. In addition, all patients' week-by-week change in mood is continuously reviewed, as is done in routine care for example at the Internet psychiatry unit of Region Stockholm.

In addition to questions about sociodemographic variables (such as age, sex, educational attainment, income and civil status), the following questionnaires are administered via the internet (the CSQ-8 in paper form [Note: All were administered online due to the covid-19 pandemic, see "Data safety and management" below.]):

Questionnaire	Outcome	Ref	SN	PRE	W	POST	3MFU
Client satisfaction questionnaire (CSQ-8)	Satisfaction with the course	(21)				x	
Generalised Anxiety Disorder 7-item Scale (GAD-7)	Anxiety	(22)	x	x	x	x	x
Patient Health Questionnaire 9 (PHQ-9)	Depression	(23)	x	x	x	x	x
Perceived Stress Scale 10 (PSS)	Stress	(24)		x		x	
12-item WHO Disability Assessment Schedule 2.0 (WHODAS 2.0)	Functional impairment	(25)		x		x	
Lifestyle behaviours	Lifestyle behaviours (tobacco, alcohol, physical activity, diet)	(26)		x		x	x

3MFU = 3-months follow-up, POST = post-intervention, PRE = pre-intervention, SN = screening, W = weekly during the course

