### ***Research question (study aims)***

The aim of this within-group study is to evaluate a CBT-based intervention similar to SC, focusing on feasibility and efficacy in Swedish primary care, with British reference data (12). The study includes a combination of patients with clinically significant levels of anxiety or depression and patients with subclinical symptoms, analyses concerning the clinical group being the primary focus of the study. The primary outcome is patient satisfaction, see below. Secondary outcomes include adherence to the protocol and effects on psychiatric symptoms in terms of anxiety and depression. Perceived stress, functional impairment and adverse events are also surveyed to make it possible to assess the relevance of the intervention for stress-related mental health problems, enable comparisons versus other protocols and ensure that the intervention is safe and does not result in unnecessary distress. Specific hypotheses are:

- Primary outcome: For patients with clinically significant symptoms, adequate satisfaction as measured using the 8-item Client Satisfaction Questionnaire (CSQ-8) and as evidenced by mean score of at least 22 points.
- Secondary outcome: For patients with clinically significant symptoms, adequate proportion of clinically significantly improved (12), in accordance with Jacobson and Truax (20). At least 1/3 of participants reporting a reliable reduction in anxiety (on the GAD-7) and a GAD-7 score below cut-off (8p) after the course. At least 1/3 of participants reporting a reliable reduction in depression (on the PHQ-9) and a PHQ-9 score below cut-off (10p) after the course.

Exploratory secondary outcomes also include:

- Adherence to the protocol, operationalised as the number of lectures attended.

[Translated from the original that was approved by the Swedish ethical review authority]

- Self-reported lifestyle behaviours at baseline, and change in lifestyle behaviours. Due to limited power, this focuses on within-group effect sizes and not inferential statistics.
- The proportion of patients in need of additional mental health interventions, as determined by a clinician interviewer after the course.
- The proportion of patients who report a perceived need of additional interventions.
- Adverse events during the intervention

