### ***Description of the research project (methods)***

#### *Design and power*

This study is a within-group trial (i.e., observational study) where 68 patients with common clinically significant psychiatric problems in terms of anxiety and depression are recruited in the primary care system of Stockholm[, Sweden]. The intervention is evaluated in terms of [satisfaction, ]adherence and self-reported symptom outcomes. Power was determined to enable the analysis of data based on a general linear model with dependent means (pre-post) with 80% power in studying effects on symptoms corresponding to  $d=0.45$  given  $\alpha=0.05$  and the expected data loss (no data at post intervention) of 40%. The effect size  $d=0.45$  was chosen on the basis of effects reported by similar interventions in British primary care (12). Up to 25 patients with subclinical symptoms (PHQ-9<10 and GAD-7<8) are also recruited for an exploratory investigation of satisfaction and preliminary efficacy in this patient group.

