#### *Evaluation and statistical analysis*

Primary outcome is the mean CSQ-8 score for patients completing this post-intervention questionnaire. Secondary outcomes that concern clinically significant improvement are based on the algorithm for reliable change as specified by Jacobson and Truax (20), combined with the established cut-offs for anxiety and depression of 8 points on the GAD-7 and 10 points on the PHQ-9 (27). Clinically significant improvement is calculated based on the last observation from each patient. Dose-response relationships and change over time are analysed using linear mixed models, if deemed suitable for the data. Linear regression is used for other continuous outcomes, and chi tests for nominal data. Within-group effect sizes are presented in terms of Cohen's *d*, and standardised effect sizes are compared to British reference data (12).

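### Care received between the end of the course and 3 months is not described as recorded, and the analysis section does not say which time points are used, so a 3-month symptom result could mix the course with later care

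*Combined protocol and SAP*

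**What the plan says.** All references are to the combined protocol and SAP.

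- **Measurements and psychometric instruments.** Each patient meets a clinician of the psychosocial team after the course, in an assessment modelled on routine care. "During this assessment, all further necessary arrangements are registered", with the kind of help noted. At the same appointment the patient reports medication changes and other treatment.
- **Same section.** "A follow-up assessment will also take place after 3 months". In the questionnaire table, the 3-month column contains GAD-7, PHQ-9 and lifestyle behaviours only. CSQ-8 is collected at POST only.
- **Research question (study aims).** One exploratory outcome is "The proportion of patients in need of additional mental health interventions, as determined by a clinician interviewer after the course". The symptom hypotheses concern scores after the course. No hypothesis concerns 3 months.
- **Evaluation and statistical analysis.** Dose-response relationships and "change over time are analysed using linear mixed models, if deemed suitable for the data". No time points are named, and there is no rule for treatment received after POST. Clinically significant improvement uses each patient's last observation, with no stated limit on how late that may be.
- **Design and power.** The sample size rests on a "general linear model with dependent means (pre-post) with 80% power", so it is a pre-to-post calculation.

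**The concern.** Further care is arranged at POST for patients judged to need it, and symptoms are measured again 3 months later. A 3-month GAD-7 or PHQ-9 mean therefore reflects the course plus whatever treatment followed. The added care is driven by symptoms: it goes mainly to patients who still have problems at POST and so have room to improve. A flat pooled curve from POST to 3 months could mean that gains lasted. It could also mean that gains faded in some patients while later care helped others.

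Arrangements registered at POST show what was planned. They do not show whether the care was taken up, or what was started afterwards. If this is not asked at 3 months, it may not be recoverable from study data.

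There is a second route. If the last observation can be the 3-month score, later care enters an outcome that carries a hypothesis (at least one third improved), although the aims set that outcome at the end of the course.

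**Working it through.** **1. The plan's own figure.** Inputs from Design and power: d = 0.45, alpha 0.05 (sidedness not stated), 80% power, and "the expected data loss (no data at post intervention) of 40" per cent.
- Two-sided paired t-test: 41 completers are needed (power 80.3%; with 40 it is 79.3%).
- 41 / (1 − 0.40) = 68.3, which agrees with the stated 68 up to rounding.
- This is a pre-post calculation, and nothing in this point changes it.

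**2. What is recorded, and when.**

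| Item | POST | 3 months |
|---|---|---|
| GAD-7, PHQ-9, lifestyle | yes | yes |
| CSQ-8 | yes | no |
| Further arrangements and their kind | yes | not described |
| Medication changes, other treatment | yes | not described |

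The section on data safety mentions interview data before and after the intervention only, so no 3-month interview is described either.

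**3. Which analyses can reach 3 months.**
- Change over time: the window is not stated. GAD-7 and PHQ-9 are collected at 3 months and no other analysis is named for them there, so including them is the natural reading, but an inference.
- Clinically significant improvement: taken literally, the last observation is the 3-month score for anyone who answers then. With 40% expected to have no POST data, 0.40 × 68 = 27.2, so about 27 of the clinical group depend on how this rule is read: last weekly score, or 3-month score if there is one.

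**4. Possible size, under assumptions.** The documents give no expected referral rate, uptake or effect of later care. Let p be the share of patients receiving further care and e the extra improvement it brings, in SD, with no effect in the rest. The 3-month within-group d then rises by p × e. Assumed ranges: p = 0.2 to 0.6, e = 0.3 to 0.8.

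| p | e = 0.3 | e = 0.5 | e = 0.8 |
|---|---|---|---|
| 0.2 | 0.06 | 0.10 | 0.16 |
| 0.4 | 0.12 | 0.20 | 0.32 |
| 0.6 | 0.18 | 0.30 | 0.48 |

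The fade that would be fully hidden is p × e divided by the post-course effect. Using the British reference effects in the background section:
- Depression, d = 0.59: 0.06 / 0.59 = 10% to 0.48 / 0.59 = 81%.
- Anxiety, d = 0.70: 0.06 / 0.70 = 9% to 0.48 / 0.70 = 69%.

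**5. The direction also depends on the assumptions.** In PHQ-9 points, pooled change = p × (change with further care) + (1 − p) × (change without). Suppose p = 0.40 and patients without further care worsen by 1 point.
- Further care gives −3: 0.40 × (−3) + 0.60 × 1 = −0.6. The worsening is hidden.
- Further care gives −1.5: −0.6 + 0.6 = 0.0. It is hidden behind a flat curve.
- Further care gives −1: −0.4 + 0.6 = +0.2. Worsening shows.

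These figures show that masking can occur. They do not estimate it.

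**The case against.** A reader might infer that the plan credits later routine care to the course and so conceals fading. The documents do not support that. The model's time points are unstated, power and symptom hypotheses are tied to the end of the course, and no claim of lasting benefit at 3 months is promised. Nor is durability shown to be the only purpose of follow-up: lifestyle behaviours are one of the three 3-month measures and have their own rationale, the scarcity of such data in Swedish primary care.

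Further objections, and what stands of each:
- *The table lists questionnaires only; the POST treatment questions are not in it either.* True, so the 3-month column alone is weak evidence. But the text places those questions at the POST appointment, and the available text describes no 3-month counterpart.
- *The study is single-arm, so no time point separates the course from natural recovery. Concurrent therapy is not excluded, and extra support is possible during the course.* This stands: stopping at POST does not isolate the course. It keeps out one further co-treatment that could be recorded.
- *Arranged care is already registered at POST, so results can be split by it.* Partly true, but uptake and later-started care are missing. The groups would also be selected on POST symptoms, so regression to the mean alone could make the referred improve and the others worsen. Such a split cannot by itself demonstrate fading.
- *CSQ-8 and the pre-post power are untouched.* This stands and limits the weight of the point.

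**Conclusion.** The point holds in a limited form. Further care is arranged at POST, no recording of care received up to 3 months is described, and the analysis section states neither a time window nor a rule for such care. If 3-month GAD-7 and PHQ-9 scores are used, the result is that of the course plus any later care, and fading could be masked. The size cannot be estimated: the range of 0.06 to 0.48 SD rests wholly on assumed shares and effects, and other assumptions leave a worsening visible.

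The consequence is confined to exploratory 3-month results, unless the last-observation rule is applied literally, in which case it reaches the clinically significant improvement outcome. The primary outcome and the sample size of 68 stand. The conclusion rests on the text available; a provision elsewhere in the plan for recording later care would remove the first part. The change is worth making because it costs almost nothing and decides what the 3-month data can support.

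**What to change.** 1. **Measurements and psychometric instruments:** add the question on medication changes and other treatment, now asked at POST, to the 3-month online questionnaire.
2. **Evaluation and statistical analysis:** name the time points for each analysis. Base course-effect analyses on data up to POST, and limit the last-observation rule for clinically significant improvement to POST or earlier, in line with the aims.
3. **Same section:** describe 3-month results, including lifestyle effect sizes, as those of the course followed by any routine care.
4. If 3-month change is split by the arrangement registered at POST, present it descriptively and warn that the groups are selected on POST symptoms and subject to regression to the mean.

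Cost: one questionnaire item, a few sentences in the analysis section, and a more cautious 3-month statement. If 3-month data are already collected, item 1 can no longer be applied to them, but items 2 to 4 need no new data.

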#### *Data safety and management*

Information from self-report questionnaires are saved as part of the patient's medical record, and also as research data using a secure data management service in accordance with the guidelines of Karolinska Institutet. Paper-form written consents and data from interviews pre- and post-intervention are stored in locked cabinets and are destroyed when transferred to a

[Translated from the original that was approved by the Swedish ethical review authority]

secure digital form. Within 2 years, the interview guides are converted to digital documents stored in a safe manner, and the paper guides are then destroyed. Due to the covid-19 pandemic, as long as necessary, the study will be conducted without physical meetings. To make this possible, secure systems with encrypted data traffic are used. During this period, informed consent to take part in the study is given via a web-based form, via a secure web platform (128-bit encryption and a personal account with two-factor authentication) that has been used in several previous clinical trials (see for example [Regional ethics review board of Stockholm application] 2014/1530-31/2). [Note: This was written in early May of 2020. The course was eventually held entirely online in accordance with this clause.] Only researchers in the project have access to the raw data, and results are presented in a way that does not make it possible to identify individual participants. Personal information that is not necessary to characterise the sample or that does not constitute the outcome of the study will not be curated or used for publication.

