### *Intervention*

Patients are enrolled in a CBT-based intervention similar to SC, in a transdiagnostic format that enables shortened clinic waiting times. The course consists of six weekly lectures where up to 50 patients participate over 90 to 120 minutes.

The intervention is primarily based on psychoeducation about stress and how the body reacts to stressors, about exercise/activity and recuperation/relaxation, the impact of behaviours and thoughts on mental health, about anxiety, depression, how to manage sudden burst of intense anxiety (panic attacks) and techniques for improved sleep. The course comprises 6 lectures with corresponding themes: (1) "Stress", (2) "Worry and anxiety", (3) "Low mood and depression", (4) "Sleep", (5) "Physical activity and mental health" and (6) "Relationships and the importance of emotions". The aim of the course is to improve the participants' ability to identify what they need to feel better, and to provide the participants with the tools necessary for them to improve their mood for the better. Structured PowerPoint presentations will be used. The course also involves written material about each lecture theme and this material includes suggestions for tailored exercises ("homework"). Participants are encouraged to read and work with the written material before and between each lecture.

The psychological intervention is led by clinicians of the psychosocial team which consist of counsellors ["kuratorer"] and psychologists with training in cognitive behaviour therapy (CBT). In order to ensure competence, all therapists except the author of the course, [name], attend a half-day introduction to the intervention and also sit in on at least one lecture led by a clinician already trained in delivering the course. All therapists receive regular supervision by the project leader [name] (and [name] by another researcher in the project) about every other week over the course of the study. Adherence is ensured by the use of a structured manual and checklists completed by the therapist after each lecture.

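### The plan files the CSQ-8, its primary outcome, in the patient's medical record and does not say that it is kept from the team being rated

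*Combined protocol and SAP*

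**What the plan says.** All references are to the combined protocol and SAP.

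- **Outcome and target.** Research question (study aims) sets the primary hypothesis for the clinical group as "adequate satisfaction as measured using the 8-item Client Satisfaction Questionnaire (CSQ-8) and as evidenced by mean score of at least 22 points". Evaluation and statistical analysis adds: "Primary outcome is the mean CSQ-8 score for patients completing this post-intervention questionnaire". There is no comparator.
- **Storage.** Data safety and management: "Information from self-report questionnaires are saved as part of the patient's medical record, and also as research data". Measurements and psychometric instruments: "The measurements are conducted using online questionnaires that are stored in the patient's digital record". Neither sentence makes an exception for any form.
- **Mode.** Measurements and psychometric instruments planned "the CSQ-8 in paper form [Note: All were administered online due to the covid-19 pandemic" and so now places the CSQ-8 with the other online forms. The schedule there has it collected once, after the course.
- **Who is rated.** Intervention: "The psychological intervention is led by clinicians of the psychosocial team". A clinician of the same team meets the patient after the course and registers what further help is needed. Satisfaction is listed among the things the patient reports in that account.
- **Access.** Data safety and management also says "Only researchers in the project have access to the raw data". It does not say whether this means the research dataset, the copy in the record, or both.

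**The concern.** Satisfaction is an opinion about a service. Patients come from this clinic's routine care, its psychosocial team gives the course, and a member of that team then assesses whether they need more. A patient who thinks the rating may be seen by that team has a reason to rate kindly. With no control group and a fixed pass mark, any such upward shift goes straight into the primary conclusion, because nothing in the design cancels it.

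The sponsor already recognises the mechanism. Recruitment uses a scheduler who is not a study therapist and gives information in advance, so that dependence on the therapist weighs less on the decision to join. No section available for review gives the primary outcome a comparable protection.

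**Working it through.** **1. Does the storage text reach the CSQ-8?** The sentence in Data safety and management covers self-report questionnaires in general, and the CSQ-8 is one. The sentence in Measurements and psychometric instruments covers online questionnaires, and the CSQ-8 became one when the paper plan was dropped. No exemption appears. On the plan's wording the CSQ-8 is therefore in the record. No sentence separately confirms that the online CSQ-8 was filed there.

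**2. Does the access sentence protect it?** Two readings are possible.
- If raw data means the research dataset, the sentence is silent on the copy in the record.
- If it means every copy, access is limited to project researchers. That still does not separate the rater from those rated. The Intervention section has the project leader supervising the therapists, another project researcher supervising the course author, and the course author counted among the therapists.

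On neither reading is the CSQ-8 explicitly kept from people who lead or supervise the course.

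**3. Number of completers.** Design and power gives d = 0.45, α = 0.05, 80% power and 40% data loss. A two-sided paired t-test needs n = 41 (power 0.803), and 41 / 0.60 = 68.3, which agrees with the planned 68. Conversely 68 × 0.60 = 40.8, so about 41 completers. This calculation concerns symptom change; the plan gives no precision calculation for the CSQ-8.

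**4. Sensitivity of the pass/fail result to a shift.** The documents give no SD for the CSQ-8, so 4 to 6 is an assumption. The true means and the shifts are also assumptions.

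SE = SD / √41. Chance of passing = P(Z ≥ (22 − true mean − shift) / SE).

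Example with SD 5, true mean 21: SE = 5 / 6.403 = 0.78. With no shift, z = 1 / 0.78 = 1.28 and the chance is 10.0%. With a 1-point shift, z = 0 and the chance is 50%.

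Chance of an observed mean of at least 22, no shift → 1-point upward shift:

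| Assumed SD | SE | True mean 20 | True mean 21 | True mean 21.5 |
|---|---|---|---|---|
| 4 | 0.62 | 0.1% → 5.5% | 5.5% → 50% | 21.2% → 78.8% |
| 5 | 0.78 | 0.5% → 10.0% | 10.0% → 50% | 26.1% → 73.9% |
| 6 | 0.94 | 1.6% → 14.3% | 14.3% → 50% | 29.7% → 70.3% |

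A half-point shift at a true mean of 21.5 brings the chance to 50% for every SD. If the true mean were 24 (SD 5), the unshifted chance is already about 99% and a shift changes almost nothing.

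**5. What the table does and does not show.** It shows that a bias of a point or less matters if the true mean lies just under 22. It does not estimate the bias, and it does not tie any size to storage in the record.

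**The case against.** A reader might infer three stronger things from these passages, and the documents support none of them.

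- **That the course leaders can read each patient's rating.** No section says who can open the questionnaire entries in the record, or that it is the working chart of the course team. Where access is mentioned, it points to researchers: the Intervention section has them reviewing the weekly answers, and Data safety and management restricts raw data to them.
- **That the two sentences in Data safety and management contradict each other.** Two stores are named, and raw data can naturally mean the research dataset, since the same sentence goes on to how results are presented. The text is unreconciled, not shown to be false.
- **That patients rated in the knowledge that staff would see the score.** Consent pages were removed before review, so what patients were told cannot be checked.

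Further objections carry some weight. Online self-completion may reduce face-to-face pressure. A clinician might find the rating useful at the closing appointment; the plan states no such use but does not rule it out. The illustration uses true means close to the threshold, where any bias looks large. Moving the CSQ-8 out of the record would not make it anonymous, so some courtesy bias could remain. The notes on the pandemic also indicate that the course has already been held.

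These objections limit the claim to a risk. They do not remove the gap: the plan puts an identifiable rating into a care record and states no barrier between it and the team being rated.

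**Conclusion.** The point holds as a risk of bias that the plan leaves open, and the remedy is a cheap improvement, not the correction of an error. As written, the CSQ-8 falls under the medical-record storage rule, no section shields it from the psychosocial team, and the access sentence does not settle the matter on either reading. Any bias would probably run upward, towards the 22-point target.

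Its size is unknown and cannot be derived from the documents. It would change the conclusion only if the true mean is near 22. The illustrative movement at a true mean of 21 (from 5.5–14.3% to 50% for a 1-point shift) rests on about 41 completers, an assumed SD of 4 to 6 and an assumed shift.

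**What to change.** In Measurements and psychometric instruments and in Data safety and management:

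1. Exempt the CSQ-8 from storage in the medical record and save it only in the research database. Storage of the other questionnaires need not change.
2. Limit access to individual CSQ-8 answers to researchers who neither lead nor supervise the course.
3. Tell patients this on the CSQ-8 page, before the first item.
4. Reword the access sentence to say which copy it covers, and state who can open the questionnaire entries that remain in the record.

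The cost is a routing setting for one form, one sentence on that form and a short protocol edit. The downside is that clinicians cannot see an individual's satisfaction score, and the mean may come out slightly lower.

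If collection is already complete, report who had access to the CSQ-8 answers and list courtesy bias as a limitation of the 22-point conclusion. The routing can then be adopted in the controlled evaluation foreseen under Significance.
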